Study Design	
International, multicentre, non-pharmacological, comparative, open-label, parallel-group, mixed Observational-Randomized Controlled Trial.
 
All the patients, who are candidate for the study will receive full information on the characteristics, potential effectiveness and side effects of the two alternatives treatments (radiotherapy and standard surgical treatment \pm RT);
 
Eligible and well-informed patients who give their consent to participate will be asked to choose among 3 alternative treatment options:
 
A. to undergo surgery (\pm RT)
 
B. to undergo definitive radiotherapy
 
C. to be randomized to either definitive radiotherapy or surgery (\pm RT).
 
As reported in the subsequent flow-chart patients who refuse randomization (treatment option c.) will be included in the Prospective Cohort Study (PCS) and will be treated accordingly to their choice (treatment option a. or treatment option b.). The same radiotherapy and surgical regimen will be administered in the PCS and in the Randomized Clinical Trial (RCT).
 
 <pre> graph TD A[Assessed for Eligibility] --> B[Excluded] A --> C[Randomised] A --> D[Allocated to Radiotherapy] A --> E[Allocated to Surgery] C --> F[Allocated to Radiotherapy] C --> G[Allocated to Surgery] D --- H[Prospective Cohort Study] E --- H F --- I[Randomised Controlled Trial] G --- I </pre> 
 
If for country specific regulation or, institutional reasons a site could not participate to both cohorts (Prospective and Randomized), it is allowed to participate only to the Prospective, non-randomized cohort.
 
In this case the Institutional Review Board (IRB)/Independent Ethics Committee (IEC) could approve only the Prospective Cohort Study.”

Sponsor	Italian Sarcoma Group (ISG) [name] www.italiansarcomagroup.org

SYNOPSIS

SACRAL Chordoma: a Randomized & Observational study on surgery versus definitive radiation therapy in primary localized disease (SACRO)

Global Study Coordinators	
Surgery Global Coordinator: Dott. [name] - Fondazione IRCCS Istituto Nazionale dei Tumori, Milano
 
Radiotherapy Global Coordinator: Dott. [name]- CNAO di Pavia

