
SYNOPSIS

SACRAL Chordoma: a Randomized & Observational study on surgery versus definitive radiation therapy in primary localized disease (SACRO)

	
 - The Distant Relapse Failure (DRF), defined for each patient as the time from randomization (RCT) or treatment start date (PCS) to the date of distant disease relapse. Local relapse, second primary malignancy or death before any distant disease relapse will be considered competing events; subjects alive and not relapsed at the time of the analysis will be censored at the last disease assessment date. Disease relapse will be determined radiologically for any appearance of new malignant lesion/s or dimensional increase of malignant lesion/s already present at the baseline assessment. - Best Response rate to definitive radiotherapy will be evaluated radiologically at end of RT, 3 months, 6 months and 12 months after radiotherapy - Time to best response rate to definitive radiotherapy will be evaluated radiologically at end of RT, 3 months, 6 months and 12 months after radiotherapy. 
- Safety endpoints
 
 - Incidence, nature, severity and seriousness of AEs, according to NCI-CTCAE, version 4.0 (see Appendix 2) - Maximum toxicity grade experienced by each patient for each specific toxicity - Percentage of patients experiencing grade 3-4 toxicity for each specific toxicity - Patients with at least a SAE - Patients with at least a suspect unexpected serious adverse reaction (SUSAR) - Adverse events will be evaluated using the NCI-CTCAE scale, version 4.0 - Post-operative morbidity evaluated according to Clavien-Dindo scale - Neurological impairment evaluated according to CTC-AE scale (version 4.0) - 
- Quality of life (QoL) endpoints
 
 - Maximum grade experienced by each patient for each specific item - Maximum grade experienced by each patient for each specific dimension associated with QoL (e.g. functional ability, emotional well-being, sexuality/intimacy, family well-being, treatment satisfaction, and social functioning) - Average grade experienced by each patient for each specific item - Average grade experienced by each patient for each specific dimension associated with QoL (e.g. functional ability, emotional well-being, sexuality/intimacy, family well-being, treatment satisfaction, and social functioning) 
Quality of Life will be assessed through validated evaluation scale

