Disease Study	Localized sacral chordoma
Target Population	Patients with a primary and localized sacral chordoma amenable to complete surgical resection and definitive radiotherapy.
Sample Size	
All patients who met the enrollment criteria will constitute the study population that will be splitted in two cohorts according to the choice of each patient. The PCS population will include all patients, who refused randomization and started A. or B. treatment options. The RCT population will include all the enrolled patients who agreed to randomization and were randomized in the RCT study.
 
The safety-QoL population will include all the enrolled patients in both cohort who received option A or B.
 
Recruitment into the RCT will continue until the estimates have become sufficiently stable or extreme to allow a clinical decision in most patients, as indicated by the increasing rate of refusals to accept randomization; recruitment into the PCS will continue until new, more promising or less devastating therapies become available.

SYNOPSIS

SACRAL Chordoma: a Randomized & Observational study on surgery versus definitive radiation therapy in primary localized disease (SACRO)

	The study will be closed when all the enrolled patients will have completed the study treatment; the database lock and the last and definitive statistical analysis will be done approximately one year after the last patient has been enrolled.
Treatments	Definitive radiotherapy (adron therapy, carbon ion radiotherapy or proton therapy) as compared to standard surgical treatment.
Inclusion Criteria	
 1. Histologically confirmed diagnosis (brachyury expression) of primary sacral chordoma, of any diameter and arising at any site from S1 to coccyx. 2. Age \geq 18 years 3. ECOG-performance status (PS) 0-2 (Appendix 5) 4. No previous antineoplastic therapy 5. Macroscopic tumor detectable at MRI/CT scan 6. Patient amenable for surgery 7. Patient amenable for RT

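### Quality of life is defined only as each patient's maximum and average grade, with no time window or scoring direction, and no separate QoL comparison is stated for the randomised cohort

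*Protocol*

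**What the plan says.** All references are to the protocol synopsis.

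- **Study Objective, QoL endpoints.** There are four. Two are maxima: "Maximum grade experienced by each patient for each specific item", and the same for each dimension. Two are averages: "Average grade experienced by each patient for each specific item" and "Average grade experienced by each patient for each specific dimension associated with QoL". The example dimensions include functional ability and treatment satisfaction. On the instrument, the text says only: "Quality of Life will be assessed through validated evaluation scale". No time point, window, baseline or change score is given. The same row does tie best response to radiotherapy to the end of treatment and to 3, 6 and 12 months.
- **Study Objective, secondary objectives.** Comparing QoL and safety between definitive radiotherapy and surgery is a stated aim.
- **Sample Size.** "The safety-QoL population will include all the enrolled patients in both cohort who received option A or B". The final analysis comes about one year after the last enrolment. Recruitment to the randomised trial (RCT) and to the prospective cohort study (PCS) ends under different rules.
- **Study Design.** PCS patients are those who decline randomisation and choose their own treatment. The study is open-label.
- **Statistical methods.** The PCS and the RCT are analysed separately, but this is described for relative efficacy. QoL is not mentioned.
- **Study Objective, safety endpoints.** One of them is "Percentage of patients experiencing grade 3-4 toxicity for each specific toxicity".

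**The concern.** The idea of a maximum grade comes from toxicity reporting, where a high grade is bad and one severe episode is what matters. Carried over to QoL, it raises three problems.

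- A maximum is taken over however many questionnaires a patient happens to complete, so it partly measures length of follow-up.
- Without a scoring direction, the maximum could be the patient's worst or best moment.
- Neither the maximum nor the average says when in the course of treatment and recovery a difference arises.

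The population adds a separate problem. QoL is self-reported in an open-label study, and part of the safety-QoL population chose its treatment. Differences between those who prefer surgery and those who prefer radiotherapy would enter any comparison made across the whole set.

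At stake is the secondary objective of comparing QoL between the two strategies, which readers will weigh alongside relapse-free survival.

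**Working it through.** The document gives no QoL standard deviation, visit schedule, visit count or sample size, so there is no planned figure to reproduce. The calculations below show the mechanism under assumed inputs.

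**1. Maximum.** Assume k standardised normal readings per patient, equal correlation ρ between visits, and no true change or treatment difference. The component shared by a patient's readings has mean zero and does not affect which reading is largest, so

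E[max] = √(1 − ρ) × m_k,

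where m_k is the expected maximum of k independent standard normals (m_3 = 0.846, m_6 = 1.267). With ρ = 0.6, √0.4 = 0.6325:

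- k = 3: 0.846 × 0.6325 = 0.535 SD
- k = 6: 1.267 × 0.6325 = 0.801 SD
- gap: 0.266 SD

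The same 3-versus-6 gap at other correlations (ρ = 0.3 to 0.7 by simulation, 400,000 draws each):

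| ρ | k = 3 | k = 6 | gap |
|---|---|---|---|
| 0.3 | 0.710 | 1.061 | 0.351 |
| 0.5 | 0.599 | 0.897 | 0.298 |
| 0.7 | 0.465 | 0.694 | 0.229 |
| 0.8 | | | (1.267 − 0.846) × √0.2 = 0.188 |

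For a categorical item with a 10% chance of the top category at each independent visit, the chance of ever recording it is 1 − 0.9^k: 10% at 1 visit, 34% at 4 and 57% at 8. Positive correlation between visits would make this rise smaller.

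**2. Where unequal counts could come from.** The lock date is set by the last enrolment, so follow-up length depends on entry date. RCT recruitment is to stop as refusals rise, while PCS recruitment goes on. If later PCS patients lean towards one treatment, that group has shorter follow-up in the combined population. Differential dropout or death would have the same effect in either cohort.

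**3. Direction.** If high is bad, the treatment with more assessments looks worse. If high is good, as it may be for functional ability or treatment satisfaction, it looks better, and the maximum is the patient's best reading.

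**4. Average.** With stable QoL its expectation is 0 for any k. With an assumed dip of −exp(−t/6) SD at month t:

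- visits at 0, 3 and 6 months: (−1 − 0.607 − 0.368)/3 = −0.66 SD
- visits at 0, 3, 6, 12, 18, 24 and 36 months: −0.31 SD

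The same patient course gives averages that differ by 0.35 SD, through follow-up length alone.

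**5. Combined population.** Let the true effect be zero, let choice alone create a difference b in the PCS, and let the PCS make up a share w of each treatment group. The unadjusted difference across both cohorts is then w × b. With b = 0.3 SD:

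- w = 25%: 0.075 SD
- w = 50%: 0.15 SD
- w = 75%: 0.225 SD
- w = 90%: 0.27 SD

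**6. Grade 3-4 percentage.** Assume the toxicity scale grades death as 5 (Appendix 2 is not shown). A patient whose only severe event of a given type is fatal stays in the denominator and adds nothing to the numerator. A patient recorded at grade 3 or 4 before dying of the same toxicity is counted.

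**The case against.** The strongest reply is that much of this may be settled in a statistical analysis plan that is not at hand, and that the figures rest on invented visit counts. Part of that stands.

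- **Pooling.** A reader might infer that the protocol plans an unadjusted pooled QoL comparison and so discards randomisation. It does not say so. The Sample Size row defines a population, and splitting, stratifying or adjusting by cohort could follow in the analysis plan. What stands is that this document names only the combined population for QoL and describes separate cohort analyses only for efficacy.
- **Visit counts.** Nothing shows that the treatments will differ in number of questionnaires. Within the RCT, a common lock date falls equally on both arms in expectation, so a gap there needs differential dropout or death. The 3-versus-6 contrast is hypothetical.
- **Average.** It is tempting to say that both summaries grow with visit count. Only the maximum does.
- **Direction.** It would go too far to state that the maximum is the best moment for some dimensions. No instrument is named, so the direction is ambiguous.
- **Fatal toxicity.** A reader might conclude that a treatment-related death lowers the toxicity rate or drops out of safety reporting. It only fails to raise one percentage. Maximum toxicity grade, adverse event severity and seriousness, serious adverse events and overall survival all still capture it.
- **Reversal.** No calculation here shows that the summaries would reverse a real treatment difference.

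The reply does not reach the endpoint definitions themselves. Maximum and average are fixed in this document, not left open.

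**Conclusion.** The point holds in this limited form. All four QoL endpoints are per-patient maxima or averages with no common window and no scoring direction.

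The maximum is biased wherever follow-up, dropout or death differs between treatments. For 3 against 6 visits the spurious gap is about 0.19 to 0.35 SD over correlations of 0.8 down to 0.3. The visit counts, the correlations and normal scores with no true change are all assumptions. The average is sensitive to timing and length of follow-up only if QoL changes over time.

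A QoL comparison made in the safety-QoL population as a whole would not be a randomised one. The size of any resulting bias depends on the PCS share and on how strongly choice is related to QoL, and neither is known.

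The grade 3-4 issue is a wording gap in one safety endpoint.

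These are secondary endpoints and the primary analysis is untouched. They do serve a stated comparative objective, so the change should be made.

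**What to change.** - Replace the maximum and average QoL endpoints with scale scores, direction stated, at fixed times or over a common window. Count time from randomisation in the RCT and from start of treatment in the PCS.
- Adjust for the baseline score where it is collected, and use a longitudinal model. A Bayesian model is acceptable and fits the design; the exact form can be left to the analysis plan.
- Make the RCT, analysed as randomised, the main QoL comparison. Report the PCS separately, or with cohort as a stratum and with adjustment.
- Keep maximum grade for CTCAE toxicity only.
- Change the toxicity percentage from grade 3-4 to grade 3 or higher.

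The cost is mainly rewording. No new data are needed if questionnaires are already given at fixed visits, which this document does not show. The real downside is that an RCT-only QoL estimate is less precise than one from both cohorts together.

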Study Objective	
Primary objective: This study is aimed at estimating the effectiveness of definitive radiotherapy as compared to standard surgical treatment for patients with primary sacral chordoma who are candidates to a complete en-bloc resection, in term of relapse-free-survival (RFS)
 
Secondary objectives: To estimate the efficacy, activity, safety, QoL of definitive radiotherapy as compared to standard surgical treatment for patients with primary sacral chordoma who are candidates to a complete en-bloc resection. To identify patients, radiological and pathological characteristics that might be used as predictors of relapse-free survival (RFS)/ progression free survival (PFS), overall survival (OS) To identify patients, radiological and pathological characteristics that might be used as predictors of treatment effects
 
Primary endpoint
 
 - The RFS, defined for each patient as the time from randomization (RCT) or treatment start date (PCS) to the date of local disease relapse, distant disease relapse, second primary malignancy or death from any cause, whichever occurred first. For patients treated with definitive radiotherapy not achieving CR as well as patients in R1/R2 after surgery not achieving a CR after post-operative radiotherapy the event for the RFS is the disease progression instead of the disease relapse. . 
Subjects not relapsed or died at the time of the analysis will be censored at the last disease assessment date. Disease relapse/progression will be determined radiologically for any appearance of new malignant lesion/s or dimensional increase of any size of malignant lesion/s already present at the baseline assessment.
 
Secondary endpoints
 
- Efficacy endpoints
 
 - Overall Survival (OS), defined for each patient as the time from randomization (RCT) or treatment start date (PCS) to the date of death from any cause. Subjects alive at the time of the analysis will be censored at the date of last contact. - Survival Post Progression (SPP), defined for each patient as the time from local disease relapse, distant disease relapse or second primary malignancy, whichever occurred first, to the date of death from any cause. SPP is equal to 0 in case of death before disease relapse. For patients treated with Radiotherapy not achieving CR as well as patients in R1/R2 after surgery not achieving a CR after Radiotherapy the starting point for the SPP is the local disease progression instead of the local disease relapse. 
- Activity endpoints
 
 - The Local Relapse Failure (LRF), defined for each patient as the time from randomization (RCT) or treatment start date (PCS) to the date of local disease relapse. Distant relapse, second primary malignancy or death before local disease relapse will be considered competing events; subjects alive and not relapsed at the time of the analysis will be censored at the last disease assessment date. Disease relapse will be determined radiologically for any appearance of new malignant lesion/s or dimensional increase of malignant lesion/s already present at the baseline assessment. For patients treated with Radiotherapy not achieving CR as well as patients in R1/R2 after surgery not achieving a CR after Radiotherapy the event for the LRF is the local disease progression instead of the local disease relapse.

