Statistical methods	This study is designed following a Bayesian statistical approach; the final objective of the bayesian statistical analysis will be to estimate a posterior probability distribution of the relative efficacy of the 2 treatment strategies being compared. To this aim, two independent, but sequential analyses are planned; the 1st one will be carried out on the PCS population (Learning data analysis) and the 2nd on the RCT population (Primary data analysis).
----------------------------	---

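### The PCS clock starts at treatment and its population keeps only patients who started, while the RCT counts everyone from randomisation, so the two estimates do not measure the same effect

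*Protocol*

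**What the plan says.** All references are to the protocol synopsis.

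- **Time zero.** Under Study Objective, the primary endpoint RFS is "the time from randomization (RCT) or treatment start date (PCS) to the date of local disease relapse, distant disease relapse" or the other listed events. OS is the "time from randomization (RCT) or treatment start date (PCS) to the date of death from any cause". LRF and DRF carry the same split ("time from randomization (RCT) or treatment start date (PCS) to the date of local disease relapse"; "time from randomization (RCT) or treatment start date (PCS) to the date of distant disease relapse").
- **Populations.** Under Sample Size: "The PCS population will include all patients, who refused randomization and started A. or B. treatment options". For the trial: "The RCT population will include all the enrolled patients who agreed to randomization and were randomized in the RCT study". The same row says that everyone meeting the enrolment criteria forms the study population, divided into two cohorts by patient choice.
- **Sites.** Under Study Design, a site that cannot take part in both cohorts for regulatory or institutional reasons is covered: "it is allowed to participate only to the Prospective, non-randomized cohort".
- **Analyses.** Under Statistical methods: "two independent, but sequential analyses are planned; the 1st one will be carried out on the PCS population (Learning data analysis". The RCT analysis comes second and is labelled primary. Both serve one stated aim, a posterior distribution for the comparison of the two strategies.

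**The concern.** A comparison of strategies begins when the strategy is assigned or chosen. The RCT follows that rule. The PCS begins later, and only for patients who got as far as treatment. If the path from decision to treatment differs between surgery and radiotherapy, the later start and the treatment condition select patients differently by arm.

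At stake is whether the two results can be read together. If the PCS and RCT ratios differ, part of the gap could come from the definitions and not from treatment or patient choice. If they agree, part of the agreement could be accidental. The RFS definition makes this more than theoretical: any enlargement of a lesion present at baseline can count as progression, so growth during the wait could be an event in the RCT, whereas in the PCS it falls before time zero.

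**Working it through.** **1. The rules side by side**

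| | RCT | PCS |
|---|---|---|
| Time zero (RFS, OS, LRF, DRF) | Randomisation | Treatment start |
| Population | All randomised | Refused randomisation and started A or B |
| Event between decision and treatment | Counted | Before time zero |
| Patient who never starts either option | Kept | In neither population |
| Patient at a PCS-only site | Not applicable | Never offered randomisation, so did not refuse it |

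The fourth row conflicts with the statement that the whole study population is divided between the two cohorts. The fifth conflicts, read literally, with the Study Design row.

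**2. Size**

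The protocol states no event rates, waits or non-start shares, so there is no figure of its own to reproduce. Everything below is an assumption, with a true ratio of 1 counted from the decision and 60 months of follow-up.

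*Events hidden by the wait.* With a constant hazard and median M months, the share with an event within w months is 1 − exp(−ln 2 × w/M).
- M = 96, w = 1: 0.7%.
- M = 36, w = 3: 5.6%.

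This is a share of patients, not a bias in the ratio.

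*Effect of the later clock on the ratio.* Take Weibull RFS, S(t) = exp(−(λt)^k), λ = (ln 2)^(1/k)/M. For patients event-free at treatment start after a wait w, the event rate is

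rate(w) = [1 − S(60+w)/S(w)] / ∫₀⁶⁰ S(t+w)/S(w) dt.

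The PCS ratio is rate(w, radiotherapy) / rate(w, surgery). Example with k = 2, M = 60:
- w = 1: 0.5114/48.105 = 0.01063.
- w = 3: 0.5335/47.133 = 0.01132.
- Ratio, with the longer wait for radiotherapy: 0.01132/0.01063 = 1.065.

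Range over M = 36, 60 and 96:

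| Wait, surgery / radiotherapy (months) | k = 1 | k = 1.5 | k = 2 |
|---|---|---|---|
| 1 / 1 | 1.00 | 1.00 | 1.00 |
| 1 / 2 | 1.00 | 1.022–1.025 | 1.032–1.033 |
| 1 / 3 | 1.00 | 1.043–1.049 | 1.065–1.067 |
| 3 / 1 | 1.00 | 0.953–0.959 | 0.937–0.939 |

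The shift is zero with equal waits or a constant hazard (k = 1). Otherwise it runs from about 0.94 to 1.07.

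*Effect of dropping non-starters in one arm.* Let a share q have h times the hazard of the rest, with M = 60 and λ = ln 2/60. With everyone kept, S(60) = (1−q)(0.5) + q(0.5^h), and person-time is [(1−q)(0.5) + q(1−0.5^h)/h]/λ. With the share q dropped, the rate is λ. The ratio of dropped to kept is then:
- q = 0.02, h = 1.5: the kept rate is 0.50293λ/0.49862 = 1.0086λ, so the ratio is 0.99.
- q = 0.10, h = 3: the kept rate is 0.5375λ/0.47917 = 1.1217λ, so the ratio is 0.89.

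The arm that loses its non-starters looks better than it is.

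**The case against.** The strongest reply is that a non-randomised cohort has no randomisation date, that treatment start is a common and defensible origin, and that the PCS is only the learning analysis. The primary analysis uses randomisation and all randomised patients. On size, the clock shift vanishes under a constant hazard or equal waits, and the non-starter effect needs an assumed imbalance between arms. All of that stands, and it limits the size of the point. It does not remove the mismatch, because both analyses serve the same stated aim and the two rules are fixed in this document, whatever the SAP adds.

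Three stronger readings are tempting, and the text does not support them:

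- *Patients who progress, become unresectable or switch while waiting are all lost from the PCS.* They are not. Anyone who refused randomisation and then started either option stays in. Only those who start neither are lost, which is a smaller group.
- *Confounding in the self-selected PCS passes into the RCT result as its prior.* The Statistical methods row calls the analyses independent as well as sequential, and does not say that the PCS posterior is the RCT prior. How the two are linked, and any discounting, may be settled in the SAP, which is not at hand. No error rate for the RCT can be derived from this text.
- *Patients from PCS-only sites are excluded.* The Study Design row plainly means them to be in the PCS. This is a conflict of wording to repair, and no numerical consequence can be shown.

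**Conclusion.** The point holds as a mismatch of time zero and population between the cohorts. The RCT estimates the effect of assignment, from randomisation, in all randomised patients. The PCS estimates an effect from treatment start in those who reached it. The likely distortion of the PCS ratio is modest: none with equal waits (or a constant hazard) and no differential non-start; about 0.94 to 1.07 for waits that differ within 1 to 3 months under a rising hazard; and 0.99 to 0.89 for one-arm non-start of 2% to 10% at 1.5 to 3 times the hazard. Waits, hazard shapes, medians and non-start shares are all assumed. The clock calculation also simplifies by following only patients who are event-free at treatment start.

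The change is worth making because it removes a possible selection by arm before the data can show whether that selection occurred.

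**What to change.** 1. Start the PCS clock for RFS, OS, LRF and DRF at enrolment, defined as the date of consent and recorded choice of A or B.
2. Define the PCS population as all enrolled patients who were not randomised, analysed by the option chosen, whether or not it was started.
3. Record for each PCS patient whether randomisation was offered. This brings PCS-only sites in explicitly and keeps true refusers identifiable.
4. Keep the present analysis, from treatment start in treated patients, as a sensitivity analysis.

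The cost is some wording, one recorded date and one flag. The protocol does not say that the choice date is now captured, so the case report form may need it. Patients who never start treatment must be followed. The PCS estimate also becomes an effect of the chosen strategy and no longer of treatment received, which is what the randomised comparison already measures.

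### QoL is analysed in a set defined by treatment received: randomised patients who receive neither option leave the QoL comparison but stay in the RFS comparison, and the arm for switchers is not stated

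*Protocol*

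**What the plan says.** The populations are set out in the protocol synopsis under Sample Size.

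- **RCT population:** "The RCT population will include all the enrolled patients who agreed to randomization and were randomized in the RCT study". No treatment condition is attached.
- **PCS population:** "The PCS population will include all patients, who refused randomization and started A. or B. treatment options". Starting treatment is already part of the definition.
- **Safety and QoL, one set:** "The safety-QoL population will include all the enrolled patients in both cohort who received option A or B".

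Study Design gives the options: "A. to undergo surgery" (with or without RT), "B. to undergo definitive radiotherapy", and a third, "to be randomized to either definitive radiotherapy or surgery". The same section describes the trial as open-label.

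Study Objective lists QoL among the secondary objectives, to be estimated for definitive radiotherapy relative to surgery. The secondary endpoints give QoL its own group, separate from safety. For RFS the clock in the RCT starts at randomisation, and Statistical methods places the primary data analysis on the RCT population.

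**The concern.** A received-treatment set is the usual choice for adverse events, since a patient cannot have the toxicity of a treatment never given. QoL has a different role here: it is one of the outcomes on which the two strategies are to be compared. Restricting that comparison to treated patients makes membership depend on a decision taken after allocation, by patients who know their allocation. If those who receive neither option differ from the rest, or are more numerous in one arm, the QoL contrast loses some of the protection of randomisation.

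The RFS and QoL results would then also describe different sets of randomised patients. That matters because a reader will want to set tumour control against QoL for the same patients. The problem is separate from any pooling of the two cohorts: it remains if the RCT is analysed alone.

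**Working it through.** The plan states no figure for this point, so there is nothing to reproduce. The check sets the population definitions against each other for each kind of randomised patient.

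| Randomised patient who… | RCT population (RFS) | Safety-QoL population | Arm in the QoL comparison |
|---|---|---|---|
| receives the allocated option | in | in | allocated and received agree |
| takes the other option | in | in | not stated |
| receives neither option | in | **out** | none |

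Only the third row is excluded. The second row is kept because the condition is receipt of either option, not of the allocated one. The text does not say how these patients are grouped. A set defined by receipt invites grouping by treatment received but does not require it. In the PCS the mismatch does not arise, because that population already requires a started treatment.

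**Share excluded (assumed values, none from the protocol).** Let r be the share of an arm that declines its allocation and c the share of those who take the other option. The share lost from QoL is q = r × (1 − c). With r = 10%:

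- c = 0: 10% × 1 = 10%
- c = 50%: 10% × 0.5 = 5%
- c = 80%: 10% × 0.2 = 2%
- c = 100%: 0%

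**Shift in one arm's mean.** Let patients in the set have mean m and those left out have mean m − d, in SD units. The mean of the whole arm is (1 − q)m + q(m − d) = m − qd, so leaving them out shifts the mean by q × d.

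| r | d (SD) | c = 0 | c = 80% | c = 100% |
|---|---|---|---|---|
| 10% | 0.3 | 0.10 × 0.3 = 0.03 | 0.02 × 0.3 = 0.006 | 0 |
| 20% | 1.0 | 0.20 × 1.0 = 0.20 | 0.04 × 1.0 = 0.04 | 0 |

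These shifts assume that switchers stay in their allocated arm; grouping them by treatment received would alter both arms' means further. The column c = 0 is the corner in which no decliner takes the other option. Here d refers to the QoL these patients would actually report on the course they followed, and it can have either sign. The bias in the contrast is the difference between the two arms' shifts, q × d in one arm minus q × d in the other. It could therefore favour either treatment or cancel.

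**The case against.** The strongest reply is that the rule is milder than it looks, and most of that reply stands.

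- **Refusers are not dropped as such.** A reader might infer that anyone who refuses the allocation disappears from QoL. The text does not support this: a patient who takes the other option has received A or B and remains.
- **Refusal may be rare.** Informed patients choose between A, B and randomisation before any allocation, so those with strong preferences can enter the PCS. That plausibly lowers refusal afterwards, though the protocol gives no rate.
- **The direction is open.** A reader might infer that surgical QoL will look better than it is, because those who fear functional loss decline surgery. But a patient who declines surgery does not suffer that loss. Analysis by allocated arm would count the QoL such patients have without surgery, not the QoL they would have had with it. The protocol gives no basis for a sign.
- **Arm assignment often belongs in the SAP.** This is fair for switchers, and silence on their arm would not be a finding by itself.
- **Some QoL items, such as treatment satisfaction, mean little in an untreated patient.** This is true of that item, but not of functional ability or social functioning, which are also listed.

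What the reply does not remove is the definition itself. The protocol fixes a treated-only set for a comparative endpoint, so an SAP that used all randomised patients would depart from the protocol. Forms not collected from untreated patients cannot be recovered later.

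**Conclusion.** The point holds in a limited form. As written, the randomised QoL comparison rests on a subset defined after randomisation, while RFS rests on everyone randomised. Patients who receive neither option are lost to QoL, and the arm for switchers is left open.

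This conclusion rests on the definitions alone and needs no assumption about rates. The size and direction of the bias do need such assumptions, and the documents supply none; the shifts shown, from 0 to 0.20 SD in one arm, are illustrative and not estimates. QoL is a secondary endpoint and the primary analysis population is not affected. The change is worth making because it replaces a stated rule with a less bias-prone one at little cost, not because a large distortion has been shown.

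**What to change.** Split the combined population in the Sample Size section of the synopsis.

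1. Keep the received-treatment set for adverse events only.
2. For QoL in the RCT, analyse all randomised patients by allocated arm, whatever treatment they received (a treatment-policy comparison). This also settles the arm for switchers.
3. Continue collecting QoL forms from randomised patients who decline, switch or stop.
4. Report PCS QoL separately, by treatment started.

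The cost is a short protocol change and additional forms, probably from few patients, some of which will be missing. The text at hand shows no QoL schedule, so the workload cannot be put more exactly. The comparison will then describe the two treatment strategies rather than the treatments actually received. If the latter is also of interest, it can be reported as a labelled supplementary analysis.
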